7.5.4 EXPECTEDNESS

Adverse events that meet the tracking criteria (CTCAE 3 or higher and are treatment-emergent) and are thought to be treatment-related will be assessed against known information for the treatment and then assessed for expectedness. Events are considered unexpected if the nature, severity, or frequency of the event is not consistent with the risk information previously described for the treatment. Physicians may be queried directly for this information. The final determination will be made using the Signal Detection process and can include input from the patient, their physician, information from the medical record, and review and discussion by XCures acting alone, on behalf of, or with partner or collaborator personnel and the VTB/vDMC members.

7.5.5 REPORTING EVENTS

Adverse events may be reported by XCures acting alone, on behalf of, or with partner or collaborator to sponsors or manufactures, to health authorities and regulatory agencies, and to the general public via publication or other form of communication.

7.5.6 REPORTING EVENTS TO PARTICIPANTS

As a patient-centric registry, safety information may be made available to new and ongoing registry patients and/or their treating physicians as well as the general public.

7.6 UNANTICIPATED PROBLEMS

7.6.1 DEFINITION OF UNANTICIPATED PROBLEMS (UP)

Unanticipated problems involving risks to participants or others to include, in general, any incident, experience, or outcome that meets all the following criteria:

- Unexpected in terms of nature, severity, or frequency given (a) the research procedures that are described in the protocol-related documents, such as the Institutional Review Board (IRB)-approved research protocol and informed consent document; and (b) the characteristics of the participant population being studied;
- Related or possibly related to participation in the research ("possibly related" means there is a reasonable possibility that the incident, experience, or outcome may have been caused by the procedures involved in the research); and
- Suggests that the research places participants or others at a greater risk of harm (including physical, psychological, economic, or social harm) than was previously known or recognized.

7.6.2 UNANTICIPATED PROBLEM REPORTING

XCures acting alone, on behalf of, or with partner or collaborator will report unanticipated problems (UPs) to the Genetic Alliance Institutional Review Board (IRB) in accordance with the IRB's policies and procedures. The UP report will include the following information:

- Study identifying information: protocol title and number;
- A detailed description of the event, incident, experience, or outcome;
- An explanation of the basis for determining that the event, incident, experience, or outcome represents an UP;
- A description of any changes to the protocol or other corrective actions that have been taken or are proposed in response to the UP.

To satisfy the requirement for prompt reporting, UPs will be reported within 10 working days of the XCures acting alone, on behalf of, or with partner or collaborator learning of the event.

7.6.3 REPORTING UNANTICIPATED PROBLEMS TO PARTICIPANTS

Unanticipated problems will be reported to registry participants that are affected by the UP within 30 days of XCures acting alone, on behalf of, or with partner or collaborator becoming aware of the problem.

8 ANALYTIC METHODS AND STATISTICAL CONSIDERATIONS

8.1 OVERVIEW OF ANALYTIC METHODS

Patient-focused precision oncology relies on bringing together several well-defined statistical methods into a framework that is focused on determining which treatment is best for a specific patient and integrating all information into a continuous-learning model. This model is hypothesis-driven at the patient-level, rather than study-level. At the study-level, XCELSIOR operates as a discovery engine using continuous learning and reassessment methods to identify factors that influence treatment response or outcomes for cancer patients. At a patient-level, the VTB objective is to provide services to patients and their physicians that delivers suggestions about the best treatment options for the specific patient using all available baseline co-variate information and develop algorithms that incorporate outcomes from similar patients, patient preferences, and global information gain assessments. Together enable precision oncology, combining individual hypotheses that combine molecular and clinical inferences from the VTB with computational approaches to classification of prognosis for individual patients.

The analysis of XCELSIOR Research Data will lead to new information about emerging signals from treatments in late-stage and recalcitrant cancer, as well as the development of new analytic methods to organize and integrate the results of patient treatment along with the underlying rationale supporting treatment recommendations and decisions.

8.1.1 CLUSTER ANALYSIS AND PATIENT CLASSIFICATION

Once patient data has been abstracted, a cluster analysis is required to organize and group patients along characteristic dimensions that are relevant to treatment response. The earliest clustering algorithm that has widely been used in medicine is k-means clustering, which uses Euclidian distance to partition groups of observations together such that the distance between group members is minimized while the distance between centers of groups is maximized. The clusters are then defined by linear partitions that form along the borders of the groups in n-dimensional space. This method has been used to create evidence-based subgroups within different tumor types, for example GBM. However, because this approach struggles with very-high dimensional analysis, other methods for reducing dimensionality may be combined, for example Principal Components Analysis, which has also been used along and in combination with k-means clustering for glioblastoma. More advanced clustering techniques will be explored as part of the methods development aims to implement the optimal strategy for patient classification for the purpose of precision oncology. This could include Bayesian Latent Class Trajectory Analysis, K-nearest neighbor in combination with Bayesian NP Clustering, deep neural networks, and/or Random Forest (Decision Tree Ensemble Method).

Brennan and colleagues (2009) used clinical information, including histopathology, treatment, and outcome with proteomic analysis of GBM samples to perform cluster analysis. They identified three major clusters, with the most important axes being PDGFR expression, EGFR expression and loss of NF1 signaling, which they then extended by analysis of genomic alterations that characterized each cluster. By clustering patients using NGS and other data, identification of likely driver mutation pathways can provide information to the VTB to recommendation of targeted therapies. The following figure from that article shows the utility of such classification schemes.

Figure 6. Unsupervised clustering of GBM. From Brennan et al., 2017.

This approach has been used by Wang and colleagues (2017a) to show three distinct subgroups of glioma based on genomic and transcriptomic profiling, that differ in their prognosis and treatment response. They term these subgroups, proneural, mesenchymal, and classical, which are characterized by transcriptional differences, as well as the presence of various tumor-associated cells in the tumor microenvironment. They further examine progression and the corresponding changes in the transcriptome of tumor cells between diagnosis and first progression. Similarly, Wang and colleagues (2017b), demonstrate that therapy alters the tumor genome through an evolutionary process and further traced the lineage of dominant tumor clones over time using Bayesian analysis. In glioblastoma, hypermutational states are common in IDH-wild type GBM following relapse after temozolomide. Hypermutated GBM has been associated with responsiveness to immunotherapy. Prior treatments, with histopathological and NGS information, are thus important co-variates for classifying patients.

For XCELSIOR, the goal is a continuously-learning model, which means that the overall patient clusters need to be recalculated continuously as new information is generated. The principal intent is that the clusters should consider clinical, panomic, and other information to build logical groupings of patients that provide informative structure for predicting baseline trajectory and likely treatment response. XCELSIOR will explore various clustering approaches common in machine learning, specifically the use of Bayesian non-parametric (NP) clustering. This approach has several advantages for this application. First, this approach functions similarly to a generalized k-means clustering model, but unlike k-means clustering Bayesian NP models 1) do not require that the covariate relationship between clusters to be zero, 2) does not require the pre-specification of the number of clusters in advance, 3) can handle high dimensional data without the need to reduce dimensionality, and 4)

make no underlying assumptions about the shape of the data (Kulis and Jordan, 2012). Bayesian NP cluster models can also incorporate new information and make updated estimates of clustering structure continuously. They can also map two different datasets onto a common group of clusters, supporting learning models that begin with other datasets.

Another valuable aspect of Bayesian hierarchical models can incorporate prospective forecasts with the nonparametric clustering with Latent Class Models (Neelon et al., 2012; Leiby et al, 2009). Multivariate latent class models can integrate multiple response variables into a single latent variable trajectory as part of a Bayesian classification model. This approach enables patient cluster models to explicitly incorporate a baseline trajectory under different treatment conditions (i.e., responders or non-responders to a treatment within a cluster along with associated response trajectory). This approach was applied in a pediatric rare disease by Lim and colleagues (2017).

Within these Bayesian models, historic information regarding outcome can be integrated into a latent variable, to create a latent class model. This approach enables the trajectory of an outcome variable with covariate information to be incorporated into the hierarchy, which is relevant to matching patients to a group for which they are both similar and likely to have a similar response. The choice of outcome variable may include several possible choices that are both context and disease-specific. These include changes to clinical parameters, such as functional performance, quality-of-life or patient reported outcomes, and adverse effects. In addition, changes to laboratory parameters, such as molecular markers, disease markers (e.g. CA 19-9), panomic tests (e.g. circulating tumor DNA), as well as imaging changes may all factor in to a response assessment. A latent response variable can integrate a variety of potential types of response into the Bayesian hierarchical model in a non-parametric manner that does not require an assumption of identical distributions of the response variable.

Another benefit to this analytic approach is that it enables the pre-specification of a response trajectory for specific patients at enrollment into the registry. This should be possible for potential response trajectories for various treatment options within an equipoise set—defined as options where the variance around the patient-specific trajectory forecast overlaps among options.

By defining evidence-based clusters that integrate clinical information, including demographics, tumor anatomic information, histopathology, prior treatment responses, with laboratory parameters including panomic information to create a grouping of patients that appropriately weights all the information available and accounts for the covariate relationships that exist between different types of information, XCELSIOR should be able to assess individual patient treatment hypotheses prospectively against response forecasts.

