All these approaches to cluster analysis allow for the iterative update and improvement of group definitions using empirical approaches. Modern methods of clustering allow for learning, identification of hidden relationships, and require fewer assumptions about the underlying structure of the data. For example, Bayesian Non-parametric approaches to clustering do not require assumptions about the number of clusters, shape of the data, or number of dimensions. Such an approach also allows updates to the confidence of the groupings based on each new observation. There have been several other relevant innovations, including advances in nearest neighbor searching algorithms, which can also be used for clustering, as well as learning neural networks, and other techniques of machine learning that can inform the grouping of patients to improve the identification of similar patients based on all available information rather than a small group of inclusion and exclusion criteria. These approaches have increasingly been used to facilitate diagnosis and prognosis for patients, which has been reviewed recently by Jiang and colleagues (2017).

It is well established that things like the location of tumor and age of onset correlate strongly with molecular features in some tumor types. Machine learning is ideal for understanding the hidden relationships between these types of data in order to build a model of patient groups. In fact, the proposed approach of Bayesian NP clustering also provides a mechanism to fit patients to clusters without needing the same or even a complete set of data for all patients. This technique allows the mapping of a new and different dataset on to clusters produced from another dataset. For example, using registry data from xCures partner, the Musella Foundation for Brain Tumor Research and Information, Inc, a cluster model can be produced and new registry data from patients collected under this protocol can be fitted to existing groupings, while also informing and updating the group structure.

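### Section 8.1.1 favours Bayesian non-parametric clustering partly because it needs no dimension reduction and assumes no data shape; neither is true in general

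*Protocol*

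**What the plan says.** Protocol section 8.1.1 starts from k-means, concedes that it has difficulty in very high dimension, and allows principal components analysis alongside it. It adds that "More advanced clustering techniques will be explored as part of the methods development aims" and lists latent class trajectory analysis, nearest neighbours combined with Bayesian non-parametric (NP) clustering, deep neural networks and random forests as possibilities.

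The section then singles one method out: "XCELSIOR will explore various clustering approaches common in machine learning, specifically the use of Bayesian non-parametric (NP) clustering". It describes this method as working like a generalised k-means and gives four advantages over k-means. The third is that it "can handle high dimensional data without the need to reduce dimensionality". The fourth is that such models "make no underlying assumptions about the shape of the data".

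Section 2.2.6 makes the same case: "Bayesian Non-parametric approaches to clustering do not require assumptions about the number of clusters, shape of the data, or number of dimensions". It refers to "the proposed approach of Bayesian NP clustering".

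The inputs are clinical and panomic, and 2.2.6 says that having far more parameters than sample items is now common in medicine. Neither section names a kernel, a base distribution or a feature set for the Bayesian NP model. Clusters are meant to inform the patient's trajectory forecast (5.1.1.1) and the equipoise sets and Leaderboard (8.1.2).

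**The concern.** A Bayesian NP mixture leaves the number of clusters open. It does not leave the rest open: it needs a within-cluster kernel, which fixes the cluster shape it looks for, and priors on the kernel parameters, which with the concentration parameter steer how many clusters appear. Two consequences contradict the two advantages.

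- **Dimension.** Each feature that does not separate the groups still adds extra parameters to any split, and the marginal likelihood charges for them. Enough such features outweigh a real group, and the posterior prefers one cluster.
- **Shape.** A symmetric kernel fits a skewed but homogeneous population better with several components than with one, so groups appear that are not there.

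The text also sits badly with itself. A method said to behave like a generalised k-means is excused from the dimension problem conceded for k-means. The practical stake is that the protocol allows a safeguard for k-means and says the favoured method does not need it.

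**Working it through.** The protocol gives no figure on this point, so there is none to reproduce. The check asks whether the two stated properties hold in a standard member of the class.

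**Inputs from the protocol.** Registry size is 10,000 (4.3) to 50,000 (synopsis). The whole research database is to be classified (8.1.6), and there are disease-specific substudies (synopsis), so smaller n is also relevant.

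**Assumptions, not from the protocol.** Dirichlet-process mixture; independent Gaussian kernels; concentration 1; normal-inverse-gamma prior with mean 0, weight k0, shape a0=2 and scale b0=1; two equal groups 2 SD apart in 5 features; all other features noise.

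**Step 1: formula.** For one feature in a cluster of n patients with sum S and sum of squares Q:

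log m = ½ ln(k0/kn) + lnΓ(an) − lnΓ(a0) + a0 ln b0 − an ln bn + constant,

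where kn = k0+n, an = a0+n/2 and bn = b0 + ½(Q − S²/kn). The log odds of the true split against one cluster are the summed differences in log m over features, plus the partition prior ln[Γ(n/2)²/Γ(n)].

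**Step 2: large-sample reading.**
- Each informative feature gains about (n/2) ln(1 + 2²/4) = (n/2) ln 2.
- The partition prior costs about n ln 2.
- Every feature, informative or not, costs c, the average charge for splitting it. Averaged over simulated noise features, the formula in step 1 gives c ≈ ln n − ½ ln k0 − 2.65.

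With p features in all, log odds ≈ 5(n/2) ln 2 − n ln 2 − pc = 1.5 n ln 2 − pc. The sign changes at p = 1.5 n ln 2 / c.

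**Step 3: check at n=1,000, k0=0.1.** Here 1.5 × 1,000 × 0.693 = 1,040 and c = 5.4. At p=5 the log odds are 1,040 − 27 = +1,013. At p=100 they are 1,040 − 540 = +500, and at p=300 they are 1,040 − 1,620 = −580. Exact calculations on simulated data with one prior gave +1,010, +504 and −616.

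**Step 4: sign change by n.**

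| n | 1.5 n ln 2 | c at k0 = 0.01 / 0.1 / 1 | features at sign change |
|---|---|---|---|
| 200 | 208 | 5.0 / 3.8 / 2.6 | 42 / 55 / 80 |
| 1,000 | 1,040 | 6.5 / 5.4 / 4.2 | 160 / 193 / 248 |
| 10,000 | 10,397 | 8.8 / 7.7 / 6.6 | 1,181 / 1,350 / 1,575 |
| 50,000 | 51,986 | 10.5 / 9.3 / 8.2 | 4,951 / 5,590 / 6,340 |

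Exact calculation over three prior settings puts the change at about 40-70, 160-255, 1,200-1,600 and 5,000-6,300. The ends move a little with the prior; k0=1 takes the upper end at n=200 to about 80.

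**Step 5: a different signal.** With n=120 and groups 1.5 SD apart in 10 features, exact log odds were +170.5 at p=10, +29.3 at p=50, −457.9 at p=200 and −3,113.8 at p=1,000. A sampler started at the true partition ended in one cluster at p=1,000. The chains were short (20 sweeps), so the exact odds are the firmer evidence.

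**Step 6: shape.** For one log-normal population with no groups, n=200, the best two-way split had log odds between +74 and +172 over the set-ups tried, against −4 to −14 for normal data. In sampler runs at n=120, a single log-normal group gave on average 6.1, 7.8 and 4.8 clusters at p=2, 10 and 50, against 2.0, 1.1 and 1.0 for independent Gaussian data. Those counts include very small clusters. Separate runs counting only clusters with over 5% of patients gave 2-3, and 1 after a log transform.

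**The case against.** The strongest reply is that nothing is fixed on these sentences. Section 8.1.1 says the method will be explored and 8.1.6 lists model types that may be used. A reader might infer that the protocol has committed to Bayesian NP clustering, since 2.2.6 calls it the proposed approach. The documents do not support that: it is the favoured candidate among several. This limits the weight of the point but does not make the two statements true.

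A second reply is that the figures test an assumed model. This stands. The protocol names no kernel, prior or feature set, and 8.1.1 wants the grouping to account for relations between covariates, which independent kernels ignore. Sparse or latent-factor variants would do better, but they do so by reducing or selecting dimensions within the model, which the third advantage says is unnecessary.

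A third reply is that small n exaggerates the problem. This also stands in part: at the planned registry size the sign change moves to thousands of features. Whole-omic inputs and small disease subsets remain exposed.

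Two further readings are tempting and should not be drawn. One is that 8.1.1 promises clusters weighted by relevance to outcome when it says the grouping "appropriately weights all the information available". It does not mention outcome relevance there, and the same section describes latent class models that do use outcome. The other is that every downstream comparison would carry the error. Section 8.1.2 has a biologist curate the options and the tumour board refine them, with the cluster model only assisting once implemented. Section 2.4.1 puts human oversight at several stages, and treatment decisions stay with patient and physician.

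**Conclusion.** The point holds as a correction of what the analysis section states. Advantages three and four in 8.1.1, and the matching sentence in 2.2.6, are untrue in general for a mixture with a kernel and priors, and they remove a precaution that the same section allows for k-means.

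The sizes in the working rest on the assumed kernel, priors, concentration, 5 informative features and 2 SD separation. They compare only the true split with a single cluster. They establish that real groups can be hidden and false ones created with inputs of the kind the protocol describes. They do not estimate how often this would happen in the registry.

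**What to change.** In 8.1.1, delete or qualify the third and fourth advantages, and make the matching change in 2.2.6. That the number of clusters need not be set in advance can stay, with a note that the concentration and priors influence it. Then state that, if Bayesian NP clustering is used:

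- high-dimensional features are reduced or selected before or within the model;
- skewed measures are transformed or given a suitable kernel;
- cluster number and membership are reported over a range of concentration and prior settings.

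A mandatory rule that clusters must first prove themselves in held-out patients is a separate design choice and is not needed to correct these statements. The cost is protocol wording and some extra analysis, with no new data. The method is described less favourably than now.

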8.1.2 EQUIPOISE OPTIONS SET AND RESPONSE MEASUREMENT

XCures acting alone, on behalf of, or with partner or collaborator currently maintains a curated list of treatment options for various advanced and recalcitrant cancers. This includes both regimens and clinical trials. In addition, treatment options suggested during consultation from VTB experts is incorporated with rationale. For example, if a patient with a tumor that is highly expressing a particular protein or gene for which there is a targeted therapy receives a suggested option from the VTB that includes off-label use for the targeted therapy due to the presence of amplification of the drug target, that becomes part of the global option set and can be matched to future patients with similar characteristics.

Matching of potential treatments to patients within clusters is accomplished through the VTB process, in which a cancer biologist at XCures acting alone, on behalf of, or with partner or collaborator curates the patient's case

information and assembles a list of possible treatment options based on rationales for review by the VTB. The VTB can refine this list or add other options. Once implemented, the patient cluster model will facilitate this process by quickly identifying options and outcomes for similar patients.

The VTB curates individual treatment option sets with analytic support to evaluate equipoise. Equipoise is defined as an overlap in the calculated treatment outcome variance among options considered in relation to similar patients defined via clustering.

Reporting of treatments will involve a filtered "Leaderboard" based on how various options have performed for different clusters of patients. The following characteristics may be calculated as the leaderboard parameters of treatment options both overall and in relation to specific patient clusters, including:

- Number of times treatment was recommended by the VTB
- Number of times a VTB-recommended treatment was chosen by a patient's doctor
- Number of patients actively on the treatment
- Efficacy signal to date using Bayesian model that can incorporate external information
- Safety/Tolerability signal to date
- Information Score

Each leaderboard item will be scored based on an iterative ranking algorithm for pairwise comparisons, which are commonly used in many fields from sports to the famous PageRank algorithm used by Google Application of a Bayesian algorithm may be employed to incorporate external information. An example of a high-performing implementation can be found in (Negahban et al., 2017). The leaderboard of treatments filtered for existing patient clusters provides a layer of expert human assessment with outcomes data for further decision analysis.

The "Information Score" of a treatment overall or in relation to specific subgroups of patients is important for developing guided search through the universe of possible treatments. This is part of the global cumulative treatment analysis, in which treatments for which a great deal of information exists would be unlikely to add significant information relative to treatments for which little information exists.

As a treatment accumulates more data, the strength of signals increases and may facilitate partitioning or rearrangement of the overall patient cluster model as information about a treatment begins to suggest which patients within a subgroup respond differently. However, as the variance associated with treatment signals declines in response to accumulating data, less well-studied options may better align with patient utility and risk tolerance as lack of information corresponds to a wide variance in potential outcomes.

